12. STATISTICS

The data will be analysed by Assign Data Management and Biostatistics GmbH. A Statistical Analysis Plan (SAP) will be finalised before database snapshot/closure providing a detailed description on the statistical methods and evaluation of study results.

An interim analysis will be performed after all subjects completed the treatment period and the final analysis will be conducted after the last subject completed the last visit.

12.1 Interim Analysis

A preliminary analysis including safety and immunogenicity data will be performed after all subjects completed Visit 5 (day 56) and therefore terminated the treatment period of the study. The purpose of this analysis is to provide highly valuable data for further Chikungunya vaccine development including the efficacy evaluation, by passive transfer of anti-Chikungunya antibodies to virus susceptible non-human primates.

Results from this interim analysis will not have any impact on the study design or the subjects during the follow up period of the study.

12.2 Methods of Statistical Immunogenicity Analysis

The immunogenicity analysis will compare the anti-Chikungunya PRNT₅₀ antibody geometric mean titre (GMT) 28 days after the last MV-CHIK vaccination in the Per Protocol (PP) analysis population between the treatment groups. GMTs and GMT ratios will be estimated by applying an analysis of variance including the factor treatment group. This will be done using log₁₀ transformed data and taking the anti-log of the resulting point estimates for the least squares means, least squares means differences and the corresponding 2-sided 95% CIs.

P-values will also be provided to compare GMTs between the treatment groups adjusted for multiple comparisons according to Tukey-Kramer. Likewise, seroconversion rates will be compared between groups.

Seroconversion will be defined as anti-Chikungunya PRNT₅₀ titres ≥ 10 .

Measles- and Chikungunya- ELISA titres will be analysed as described above.

In addition, the long-term stability of anti-Chikungunya antibodies determined by PRNT₅₀ and ELISA, 6 months and one year after the first immunisation, will be analysed compared between the five treatment groups.

12.3 Methods of Statistical Safety Analysis

The analysis of safety will be performed by means of descriptive measures in the Safety Population. Solicited and unsolicited AEs (local and systemic) will be analysed descriptively.

AEs and concomitant diseases will be coded using the MedDRA coding dictionary.

Solicited AEs (reactogenicity):

Solicited local and systemic AEs gathered by the subjects' diaries will be summarised for the 7-day period, by AE grading (mild, moderate, severe) and by treatment group. The number and percentage of subjects with AEs will be presented. Fisher exact tests will be provided for a comparison of AE rates between treatment groups in summary tables.

Unsolicited AEs:

Separately, the number and percentage of subjects with unsolicited/spontaneous adverse events (AEs), medically-attended AEs (MAEs) and serious adverse events (SAEs) will be presented for each treatment group overall, and by system organ class/preferred term, by AE grade, and relatedness. Fisher exact tests will be provided for a comparison of AE rates between treatment groups.

Laboratory values and vital signs as well as changes in laboratory values from baseline will be analysed descriptively by time point and treatment group.

12.4 Determination and Justification of Sample Size

A formal sample size calculation was not conducted. The sample size of 60 subjects has been determined based on prior experience in evaluating the safety and immunogenicity of vaccines and is typical for early phase clinical studies. Sample size for this study was determined on grounds of feasibility and common practice in similar trials.

12.5 Analysis Populations

12.5.1 Safety Population

All safety analyses will be based on the safety population, defined as subjects who entered into the study and received at least one IMP administration. All analysis based on the Safety Population will be carried out using the actual treatment received.

12.5.2 Modified Intent-to-Treat (mITT) Population

The secondary immunogenicity analyses will be based on the modified ITT population. The modified intent-to-treat (mITT) analysis population is defined to include all subjects randomised who receive at least one IMP administration. Subjects will be analysed according to the treatment group they had been allocated to, rather than by the actual treatment they received.

12.5.3 Per-Protocol (PP) Population

As a primary analysis, immunogenicity will be assessed on the per-protocol (PP) population. The PP population includes subjects without protocol deviations that could impact immune response. Examples that may lead to exclusion from the PP population are provided here (further criteria may be defined in the SAP):

- Immunosuppressive drugs: Use of corticosteroids (excluding topical preparations) or immunosuppressive drugs within 30 days prior to first IMP administration, or anticipated use during the trial.
- Subjects with any confirmed immunosuppressive or immunodeficient condition, including human immunodeficiency virus (HIV), hepatitis A, B or C infection or a family history of congenital or hereditary immunodeficiency
- Subjects who received the wrong or no IMP

These criteria for potential protocol violation are identified at the time of planning the study. However, during the course of the trial unforeseen events may occur or new scientific knowledge may become available, therefore final decisions on whether any protocol violation could impact immune response and thus lead to exclusion from the PP population will be made by the sponsor on a case by case basis in a blinded manner (and prior to study unblinding). Sample testing issues may also lead to exclusion from the PP population for particular time points.

12.6 Statistical Analysis Plan

A Statistical Analysis Plan (SAP) will be written and finalised prior to any lock of the study database. The SAP will provide a detailed description of the statistical methods and expand on the details provided in the protocol. Additional analyses may be added.

12.7 Missing Data

All attempts will be made to prevent missing data and generally, missing will not be imputed, and analysis will be limited to observed values. However, for missing data in AE evaluation (e.g. missing information about severity or causality) a worst-case approach will be applied.

13. QUALITY CONTROL AND QUALITY ASSURANCE

The trial will be conducted in accordance with the current approved protocol, ICH GCP guidelines, relevant regulations and standard operating procedures.

13.1 Periodic Monitoring

A designated Clinical Research Associate (CRA) will monitor study progress by scheduling and performing on-site study visits throughout the study including site initiation visit, several site monitoring visits and site close out visit. At regular intervals throughout the study monitoring visits will be performed to verify completeness, accuracy and consistency of data in the eCRFs, protocol adherence, adherence to GCP and the applicable regulatory requirements. Frequency and scope of source data verification will be determined before study start and detailed in the Monitoring Plan.

Therefore, the monitor must have access to all source records needed to verify the entries on the eCRFs. The investigator will cooperate with the monitor to ensure that any discrepancies identified are resolved.

The periodic monitoring will be performed by Celerion, [name]
Tel: 

13.2 Audit and Inspection

Upon request, the investigator will make all study-related source data and records available to a qualified quality assurance auditor mandated by the sponsor or to regulatory inspectors.

The investigator or designee should contact the sponsor/CRO immediately upon announcement of an audit by the regulatory authority. He/she further agrees to fully cooperate with regulatory authorities and participate with audits conducted at a convenient time in a reasonable manner.

The main purposes of an audit or inspection are to confirm that the rights and welfare of the subjects have been adequately protected, to assess whether ethics, regulatory and quality requirements are met and to verify that all data relevant for the assessment of safety and immunogenicity of the investigational product have appropriately been reported to the sponsor.

14. ETHICS

14.1 Ethical Conduct of the Study

This study will be conducted in compliance with relevant regulatory requirements, ICH GCP guidelines of the Declaration of Helsinki for biomedical research involving human subjects and the EU directive 2005/28/EC.

14.2 Independent Ethics Committees (IEC)

Prior to initiation of the study, the protocol, subject informed consent form, any other written information to be provided to the subject, any proposed advertising material, investigator's brochure (IB), information about payments and compensation available to subjects if not mentioned in the subject information, investigator's current CV and other documentation evidencing qualifications, and other documents as required by the independent ethics committee should be submitted.

Written approval/favourable opinion must be obtained from the IEC prior to commencement of the study. This approval should include a statement that these documents comply with GCP requirements and must identify the documents and versions reviewed.

During the trial, the investigator must promptly report the following to the IEC: amendments to the protocol, updates to IB, unexpected SAEs where a causal relationship cannot be ruled out, notes of administrative changes, deviations to the protocol implemented to eliminate immediate hazards to the trial subjects, new information that may affect adversely the safety of the subjects or the conduct of the trial, annually written summaries of the trial status, and other documents as required by the local IEC.

Amendments must not be implemented before approval/favourable opinion, unless necessary to eliminate immediate hazards to the subjects.

14.3 Regulatory Authority

The regulatory authority will receive the protocol, amendments, reports on SAEs, and related relevant safety information, including the final report according to EU Directive and national regulations.

Written approval/favourable opinion must be obtained from the regulatory authorities prior to commencement of the study and for all substantial amendments to the original documents before implementation.

15. DATA HANDLING AND RECORD KEEPING

15.1 Source Data and Records

Source documents are where data are first recorded and from which subjects' eCRF data are obtained. These include, but are not limited to, original charts (subjects' records), laboratory and pharmacy printouts, diaries, and data from automated instruments. On all trial-specific documents, other than the signed consent, the participant will be referred to by subject number, not by name.

At least the following data will be documented in the source records:

- Study identification, date of subject's study entry and termination
- Subject number
- Documentation of informed consent procedure
- Date of each study visit
- Medical history, demographic data
- Any examination findings, including local injection site reactions
- Adverse events
- Concomitant medication intake
- Early withdrawal date and withdrawal reason, if applicable
- Treatment dates
- Completed subject diaries

Source data entries must be made in accordance with GCP and local requirements.

The investigator will permit study-related monitoring, audits, IRB/IEC review and regulatory inspections, by providing direct access to source data. Source records should be preserved for the maximum period of time required by local regulations.

15.2 Access to Data

Direct access to source data and documents will be granted to authorised representatives from the sponsor, host institution and the competent authorities to permit trial-related monitoring, IRB/IEC review, audits and inspections.

15.3 Data Collection

During each study visit, the investigator will collect and maintain notes in the subject's study records to document all procedures, significant observations and assessments, which are regarded as source data. Additionally, diaries and laboratory result reports signed and dated by the investigator, have to be kept within the subject's records. Changes to information in the study record and other source documents will be initiated and dated on the day the change is made. All documents will be stored safely under confidential conditions.

15.4 Electronic Case Report Forms (eCRFs)

15.4.1 eCRF Entries

Information from the subjects' study records and other source documents will be entered into a 21 CFR Part 11-compliant validated electronic Case Report Form (eCRF) as soon as possible after each visit. The participants will be identified by a unique trial specific subject number. The name or any other identifying detail will NOT be included in the eCRF.

Entries and corrections in the eCRF may only be performed by the investigator or authorised study site staff via personal user account and password for access. This password must be kept confidential and must only be used by the person to whom it was assigned to ensure that each entry/change can be allocated to the person who performed the entry/change.

An automatic audit trail will log each data entry/change performed in the eCRF.

The eCRF system includes internal quality checks, to identify data that appear inconsistent, incomplete or inaccurate. Maintenance of the eCRF and the study database will be performed by the data management centre at Assign Data Management and Biostatistics GmbH.

15.4.2 Changes to eCRF Data

Necessary data changes of the eCRF data may be identified as follows:

Entries are checked by the eCRF during data entry or when the eCRF page has been submitted/saved. If the data does not fulfil particular quality criteria, a message will specify the type of problem and assist in its correction.

Monitors may ask for correction of data during monitoring (e.g., if the eCRF entry does not match the source data).

Computerised data-check programs and/or manual checks will identify clinical data discrepancies. Corresponding queries aiming at the resolution of these discrepancies will be created within the eCRF system and the study site will be informed about new issues to be resolved on-line.

All discrepancies will be resolved on-line directly by the investigator or by authorised staff.

As long as an eCRF page is not locked, required data changes can be conducted by the investigator or authorised site staff at any time.

15.4.3 eCRF Entry Validation

The principal investigator or the authorised delegate will thoroughly review the eCRF data and will finally certify the contents of the eCRF by electronically signing the eCRFs within the data capturing system directly. If a correction was made to the eCRF data after the investigator's approval, the certification must be repeated after the changes were performed.

15.5 Confidentiality of Subject's Data

The investigator will ensure that all subject's information obtained during the conduct of the study will be kept confidential maintaining subject's anonymity.

On eCRFs or any other documents submitted to the sponsor, subjects will only be identified by subject number and therefore remain confidential in all reports or publications related to the study. Documents revealing subject's identification, e.g. subject identification log and original informed consent forms, will be maintained by the investigator in strict confidence, except to the extent necessary to allow checking by CRAs, the Sponsor or competent authorities.

15.6 Record Maintenance, Archiving and Destruction

The investigator is responsible for compiling and keeping all essential documents in the Investigator Site File (ISF) during the study and for the maximum period of time in accordance with ICH GCP guidelines and local regulatory requirements.

The ISF has to be stored in a safe and secure location with restricted access to staff personnel only and will include all essential documents like the clinical protocol, competent authorities' approvals, original informed consent forms, source data, IMP dispensing and accountability logs, subjects' logs and all correspondence pertaining to the study.

The investigator will agree to archive the study documentation and will not dispose of any records relevant to this study without prior written permission from the sponsor. If an investigator moves, withdraws, or retires, the responsibility for maintaining the records may be transferred to another person upon sponsor's agreement.

The sponsor or their representative will notify the investigator when study documents need no longer be retained.

16. CHANGES IN THE CONDUCT OF THE STUDY

16.1 Protocol Amendments

Any proposed changes to the protocol must be covered in a written amendment to the protocol and submitted to the appropriate ethics committees or regulatory authorities. Amendments may only be implemented after approval of the appropriate ethics committees or regulatory authorities has been obtained except where necessary to eliminate apparent immediate hazard to subjects.

16.2 Study Termination

If the sponsor or the investigator decides to terminate the study before it is completed, they will notify each other in writing stating the reasons for early termination. In terminating the study, the sponsor and the investigator will ensure that adequate consideration is given to the protection of the subjects' interest. The investigator, sponsor or CRO will notify the relevant ethics committee and regulatory authority in writing in accordance with local requirements. Documentation will be submitted for filing in Central File and Investigator File.

17. DEVIATIONS FROM THE PROTOCOL

17.1 Relevant Protocol Deviations

A protocol deviation is any noncompliance with the clinical trial protocol, ICH GCP, manuals or local requirements. The noncompliance may be either on the part of the subject, the Investigator, or the study site staff. Consequently, corrective actions are to be developed and implemented promptly.

Important protocol deviations are deviations that might significantly affect the completeness, accuracy and/or reliability of the study data or that might significantly affect a subject's rights, safety or well-being.

Inclusion of subjects not satisfying the entry criteria will be subject to prior discussion with the sponsor and written approval from the sponsor. Subjects developing exclusion criteria during the study will be withdrawn, exceptions need prior discussion and written approval from the sponsor.

All protocol deviations will be listed in the study report and assessed as to their influence on the quality of the study analysis. No deviations from the protocol of any type will be made without complying with all the ethics committee's or regulatory authority's established procedures in accordance with applicable regulations.

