7. PARTICIPANT IDENTIFICATION

7.1 Trial Participants

Healthy male and female volunteers will be screened for inclusion and exclusion criteria and randomised to one of 5 treatment groups in case of eligibility.

60 subjects will be enrolled if all of the following inclusion criteria and none of the following exclusion criteria apply:

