7.3 Exclusion Criteria

The subject may not be enrolled in the study if any of the following applies:

1. Participation in another clinical study (including exposure to an investigational medicinal product or device) within one month before the screening visit or planned concurrent participation in another clinical study before completion of the treatment period (day 56)
2. History of immunodeficiency, known human immunodeficiency virus (HIV) infection or current hepatitis B/C infection
3. History of drug addiction including alcohol dependence within the last 2 years
4. Inability or unwillingness to avoid intake of more than around 20g alcohol per day during 48 hours after each vaccination (equals roughly 0.5 L beer or 0.25 L of wine)
5. Vaccination within 4 weeks prior to first vaccination or planning to receive any non-study vaccine until end of treatment period (day 56)
6. Prior receipt of any Chikungunya vaccine
7. History of moderate or severe arthritis or arthralgia within the past 3 months prior to Screening Visit
8. Recent infection within 1 week prior to Screening Visit (possibility of deferral)

9. Blood donations including plasma donations, 90 days prior to Screening Visit and anticipated blood, plasma, tissue, sperm or organ donation, throughout the study until end of treatment period (day 56)
10. Clinically relevant history of renal, hepatic, gastrointestinal, cardiovascular, respiratory, skin, haematological, endocrine, inflammatory, autoimmune or neurological diseases or clinically relevant abnormal laboratory values, that in the opinion of the investigator may interfere with the aim of the study
11. History of neoplastic disease (excluding non-melanoma skin cancer that was successfully treated) within the past 5 years or a history of any haematological malignancy
12. Behavioural, cognitive, or psychiatric condition that in the opinion of the investigator affects the ability of the participant to understand and cooperate with the study protocol
13. History of severe adverse reactions to vaccine administration, including anaphylaxis and related symptoms, such as urticaria, respiratory difficulty, angioedema and abdominal pain to vaccines, or history of allergic reaction likely to be exacerbated by any component of the vaccine
14. History of anaphylaxis to drugs or other allergic reactions, which the investigator considers compromising the safety of the volunteer

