8.9.2 Replacement of Subjects

Subjects who are discontinued before randomisation will be regarded as screening failures and screening will be continued until 60 subjects will be randomised.

Subjects who withdraw or are withdrawn after randomisation will not be replaced. This may result in a decreased number of subjects in the predefined sample size.

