2.9 Protocol Deviations

Protocol deviations will be collected only for the preliminary analysis. A listing of the potential protocol deviations will be prepared by Assign Data Management and Biostatistics GmbH using information from the eCRF documentation and monitoring reports. These protocol deviations will be classified into major or minor protocol deviations based on their possible impact on the study results in a Blind Data Review Meeting (BDRM) prior to the preliminary analysis attended by Assign Data Management GmbH and Themis Bioscience GmbH (sponsor).

Major protocol deviations will include but are not limited to the following:

- Subjects with any confirmed immunosuppressive or immunodeficient condition, including human immunodeficiency virus (HIV), hepatitis A, B or C infection or a family history of congenital or hereditary immunodeficiency
- Subjects who received the wrong or no IMP
- Subjects who received less than the protocol-defined number of vaccinations
- Subjects who received a wrong dose other than they were randomized to
- Subjects who entered the study even though they did not satisfy the entry criteria
- Subjects with substantial time window violations on vaccination visits
- Subjects who received an forbidden prior or concomitant medication
 - Immunosuppressive drugs: Use of corticosteroids (excluding topical preparations) or immunosuppressive drugs within 30 days prior to first IMP administration, or anticipated use during the trial
 - Treatments with non-study licensed vaccines within 4 weeks prior to first study vaccination until the end of the treatment period (day 56)
 - Receipt of blood products or immunoglobulins within 120 days prior to the Screening Visit or anticipated receipt of any blood product or immunoglobulin before completion of the treatment period (day 56)
- Further protocol deviations that could impact immune response that have not been described above

Adapted from:

STAT03_A Statistical Analysis Plan

Version 6.0, Effective Date 16-Feb-2018

Confidential and intellectual property of Assign DMB. No part of this document or its contents may be duplicated, referenced, published or otherwise disclosed in any form or by any means without prior written consent of Assign DMB.

Page 12 of 29

06CJDX

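### Protocol 17.1 allows ineligible subjects to be included with prior sponsor approval, which contradicts 7.1, 7.3 and 8.2 and may cost an unreplaced per-protocol slot

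*Combined protocol and SAP*

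**What the plan says.** The entry rule in the protocol has no exceptions. Section 7.1 reads: "60 subjects will be enrolled if all of the following inclusion criteria and none of the following exclusion criteria apply". Section 7.3 opens its list with: "The subject may not be enrolled in the study if any of the following applies". Section 8.2 assigns 60 eligible subjects at Visit 1, and 8.5.1 has the criteria checked again that day, before randomisation.

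Section 17.1 opens another route: "Inclusion of subjects not satisfying the entry criteria will be subject to prior discussion with the sponsor and written approval from the sponsor". The next sentence gives a similar sponsor-approved exception for subjects who develop an exclusion criterion during the study. The section then closes with a general limit: "No deviations from the protocol of any type will be made without complying with all the ethics committee's or regulatory authority's established procedures". Section 16.1 adds: "Any proposed changes to the protocol must be covered in a written amendment to the protocol", and such changes need approval before use unless they remove an immediate hazard.

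On the analysis side, SAP 2.9 lists among the major deviations: "Subjects who entered the study even though they did not satisfy the entry criteria". It makes no exemption for approved cases. Protocol 12.5.3 says: "As a primary analysis, immunogenicity will be assessed on the per-protocol (PP) population". On replacement, 8.9.2 says: "Subjects who withdraw or are withdrawn after randomisation will not be replaced". The same section treats a subject stopped before randomisation as a screening failure and continues screening until 60 are randomised.

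**The concern.** Because the approval must come beforehand, the 17.1 sentence describes a planned exception and not the handling of an error found later. It leaves open which criteria may be waived. For a live attenuated recombinant virus in healthy volunteers, that includes criteria written to protect the subject, such as a history of immunodeficiency (criterion 2) or of anaphylaxis to vaccines (criterion 13).

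The analysis plan then treats the approved subject as a major deviator. Any resulting loss from the primary population would be avoidable: the same volunteer, stopped before randomisation, would have been a screening failure and the place would have gone to an eligible person. The sponsor that approved the inclusion also makes the later decision on per-protocol membership.

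**Working it through.** **The entry rules side by side**

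- 7.1, 7.3 and 8.2: a subject who fails any criterion is not enrolled, and only eligible subjects are randomised.
- 17.1: a subject who fails a criterion can be included once the sponsor has discussed it and approved in writing.
- 16.1: a change to the protocol goes through a submitted and approved amendment. A standing permission to set criteria aside for individuals fits poorly with this.
- 17.1, last sentence: ethics committee and regulatory procedures apply to every deviation. This neither withdraws the waiver nor names anyone besides the sponsor who must approve it.

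For a subject known to be ineligible at Visit 1, the first and second rules give opposite answers.

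**What happens to a waived subject in the analysis**

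1. SAP 2.9 classes the subject as a major deviator. Its closing item refers to further deviations that could affect the immune response, which suggests that the listed ones are presumed able to do so.
2. Under protocol 12.5.3 and SAP 2.9, exclusion from the per-protocol set depends on whether the deviation could affect the immune response. The sponsor decides this case by case, before unblinding. Exclusion is therefore possible but not automatic. Immunodeficiency is one of the examples that 12.5.3 gives.
3. If the subject is excluded, no rule refills the place.
4. The mITT population keeps the subject, and SAP 5 analyses immunogenicity in both populations.

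**Size of the loss if exclusion follows**

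The plan offers no figure to reproduce, since protocol 12.4 and SAP 1.4 say that no formal sample size calculation was done. The one check available is 5 groups × 12 = 60, which agrees.

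The standard error of a difference in mean log10 titre is proportional to √(1/n₁ + 1/n₂).

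- No loss: √(1/12 + 1/12) = 0.4082
- One lost in one arm: √(1/11 + 1/12) = 0.4174; ratio 1.022, or +2.2%
- Two lost in one arm: √(1/10 + 1/12) = 0.4282; ratio 1.049, or +4.9%

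Allowing also for the fall in residual degrees of freedom (55 to 54), the Tukey-Kramer 95% half-width for one loss goes from 1.151 to 1.178 SD, and the unadjusted half-width from 0.818 to 0.837 SD. Both rise 2.3%. For two losses both rise 5.0%.

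The documents give no SD for log10 titre. Over an assumed range of 0.3 to 0.6, the Tukey-adjusted multiplier on a GMT ratio moves with one loss from 2.22 to 2.26 (SD 0.3) and from 4.91 to 5.09 (SD 0.6).

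Each arm enters 4 of the 10 pairwise comparisons, so these figures apply to those 4.

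**The case against.** The best defence is that 17.1 is a control and not a licence: it stops the site from deciding alone, and its last sentence puts every deviation under ethics committee and regulatory procedures. Sections 16.1 and 17.2 (serious-breach reporting) add further checks. This stands as a softener, and it means that a reader who infers that sponsor approval is the only gate goes too far. It does not resolve the contradiction, because 17.1 still presupposes that inclusion can be approved and 7.1 and 7.3 say that it cannot.

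Four other strong readings are not supported.

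- *Each waiver wastes a primary-analysis slot.* Major status alone does not exclude. Some criteria, such as a direct relationship with the sponsor or study team (criterion 20), have no evident link to titre. As printed, SAP 2.11.3 defines the per-protocol set as *including* subjects with relevant major deviations, which is a separate conflict with 12.5.3.
- *The waiver opens every safety criterion equally.* Pregnancy and immunosuppressive drugs are poor examples. Section 8.11.4 allows vaccination only after a negative pregnancy test, and 9.10.2 separately disallows immunosuppressive drugs in the stated window.
- *The sponsor could steer the result.* Deviations are classified at a blinded meeting that the data-management CRO also attends. The sponsor would know that it had granted a waiver, but the blind prevents it from favouring an arm.
- *The safety analysis loses subjects.* A waived and vaccinated subject stays in the Safety Population under 12.5.1.

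It is also fair to say that no waiver is documented or forecast, and that there is no power target to miss.

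**Conclusion.** The contradiction between 17.1 and sections 7.1, 7.3 and 8.2 is on the page and should be removed. The case rests on consistency and subject protection, not on power. The statistical cost is conditional and small: 2.2% on the standard error of the affected pairwise differences for one lost subject and 4.9% for two. These figures assume 12 per arm, no other losses, a common variance and exclusion of the waived subject from the per-protocol set. A reader might infer that a waiver necessarily removes a subject from the primary analysis. The documents support only that it may, subject to the blinded case-by-case decision.

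**What to change.** Delete the entry-waiver sentence in 17.1 and put in its place text such as: *Subjects who do not satisfy all entry criteria at Screening and Visit 1 are not randomised. They count as screening failures under 8.9.2, and screening continues until 60 subjects are randomised. Eligibility errors found after randomisation are reported as protocol deviations.* For entry, the SAP 2.9 item then covers errors only.

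Two related passages should be settled in the same revision:

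- The next sentence of 17.1 says that subjects who develop exclusion criteria will be withdrawn unless the sponsor approves an exception. Section 8.9 says that subjects may be withdrawn, for a listed subset of those criteria, after discussion between investigator and sponsor. The two must be reconciled.
- The word *including* in SAP 2.11.3 must be reconciled with protocol 12.5.3, so that it is clear which subjects leave the per-protocol set.

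The cost is short text in a protocol amendment and a SAP revision, and possibly a few more volunteers screened. The number randomised stays at 60.
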